Sample Size Calculation. The primary efficacy measure will be change in PANSS total score from baseline to each visit. Based upon a preceding proof-of-concept study (Feifel et al. Biological Psychiatry, in press) with effect sizes (cross-over design) range from .40 to .53. An estimated sample size of 24 in the placebo group and 48 in the oxytocin group (24 in each dose group) is required to achieve 85% power to detect an effect size of 0.3 for time-averaged main treatment effect (Cohen's d for standardized mean difference between oxytocin and placebo treatment groups) using 6 repeated measurements having a AR(1) (first order autoregressive) covariance structures and assuming the correlation between observations on the same subject is 0.5, and the alpha level (Type I error rate) is 0.05 in a 2-sided test (Hintze, 2008). If we ignore the repeated measures design, an effect size of 0.5 will be detected with the same alpha and beta for the same sample size of 80 patients in the ratio of 2:1 for oxytocin:placebo.

The proposed sample size includes considerations for a single pre-specified, planned interim analysis for futility stopping based on conditional power (CP) (stochastic curtailing method) (Halperin et al., 1982; Lan et al., 1982) or an equivalent stopping boundary on interim Z-test value (B-value) (Lan and Witts, 1988). This interim futility analysis will be performed and reviewed by an external statistical consultant [name] when 50% of the enrolled patients complete 6 weeks of follow-up. The adjusted critical value for an overall alpha of 0.05 (2-sided) in the final analysis is 0.0515 with resulting power 84.6% to detect a specified effect size of 0.3 or greater with 80 patients in the ratio of 2:1 for oxytocin:placebo (See Interim Analysis Plan below).

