Futility Interim Analysis Plan. This randomized, double-blind study adopts an adaptive design with a single pre-specified, planned, unblinded interim analysis for futility stopping based on conditional power (CP) (stochastic curtailing method) (Halperin et al., 1982; Lan et al., 1982) or an equivalent stopping boundary on interim Z-test value (B-value) (Lan and Witts, 1988). The purposes of this formal interim analysis are to assess CP levels which are the probability of reaching statistically significant treatment difference at study end given the interim results. To avoid inflation of Type I error, no early stopping for efficacy is planned in this study. The unblinded data will be only available to external statistician [name] and not the PIs or other study staff.

It is well known that futility termination will reduce the Type I error rate (alpha) and inflate the Type II error rate (beta =1 minus power of the test), with the level of beta inflation bounded by P_{L0} , the probability of stopping for futility under the null hypothesis of no treatment effect (Lan et al., 1982; Lachin 2005). In order to maintain the design Type I error rate (alpha) at 5% and power close to 85%, we use an iterative procedure to determine the CP utility boundary values and the adjusted Z-test critical value in the final analysis, with 60% (P_{L0}) chance of stopping for futility under the null hypothesis. This provides: 1) a CP futility stopping boundary value equal to 0.3 at 50% enrollment (i.e. stop the trial if CP observed < 0.3) under the original design assumption (see Sample Size Calculation), 2) an adjusted Z-test critical value of 1.947 (ZF) for declaring significant treatment effect in the final analysis (or $P \le 0.0515$), and 3) an overall power of 84.6%, i.e. 15.4% overall Type II error rate with 3.1% false negative error rate at interim look and 12.3% probability of continuing the trial and failing to reject the null hypothesis (false negative error rate) at study end.

In summary, we provide the following futility stopping rule for assessing interim results at 50% enrollment:

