- 1. A recommendation to stop the trial for futility if CP value for comparing combined oxytocin vs. placebo (i.e. the probability that final study results will be statistically significant given interim data) is less than 30% under the original design assumption. An equivalent boundary for interim Z-test value is 0.253 (interim P>0.800), interim B-value ≤ 0.179, or if equivalently interim drift parameter estimate ≤ 0.358.
 - a. If futility stopping criteria are met for the combined oxytocin group, we will examine CP and interim Z-test value for each dose (vs. placebo) to check if both dose groups meet a similar stopping criterion CP <0.3 (or P>0.800) for an overall alpha of 5% and an adjusted power of 80%.
 - b. In case of dropping only 1 dose arm and reallocation of remaining subjects to another arm we will use a fixed weighted Z-test method to protect the Type 1 error (Cui et al., 1999; Lan et al., 2005).
- 2. To declare the treatment effect significant if p-value computed at study end (N=72) is less than 0.0515.

This futility interim monitoring plan will include a vigorous data quality control to ensure successful signal detection in potential treatment effects. In addition to verifying validity of study design assumptions using the unblinded interim data, we will perform blinded, ongoing assessments of inconsistencies in the efficacy outcome measures, inter-relationships between efficacy variables, missing data patterns, and will implement a data management plan that has real-time capability to detect, query, and address data issues in the study.

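### The futility rule equates conditional power below 0.30 with interim Z 0.253, but at the drift behind the plan's other boundary figures conditional power at that Z is 0.351

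*Combined protocol and SAP*

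**What the plan says.** All the relevant text is in Section 9.

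- Sample Size Calculation states that 24 placebo and 48 oxytocin patients "is required to achieve 85% power to detect an effect size of 0.3 for time-averaged main treatment effect", "using 6 repeated measurements having a AR(1) (first order autoregressive) covariance structures and assuming the correlation between observations on the same subject is 0.5", with two-sided alpha 0.05. The following paragraph reports the design after allowing for the futility look, "with resulting power 84.6% to detect a specified effect size of 0.3 or greater with 80 patients in the ratio of 2:1".
- Futility Interim Analysis Plan sets "a CP futility stopping boundary value equal to 0.3 at 50% enrollment (i.e. stop the trial if CP observed < 0.3", to be computed "under the original design assumption (see Sample Size Calculation". It gives a 60% "chance of stopping for futility under the null hypothesis", a final critical value of 1.947, overall power of 84.6%, and a type II error made up of "3.1% false negative error rate at interim look and 12.3% probability of continuing the trial and failing to reject the null hypothesis".
- Stopping rule item 1 repeats the 30% CP threshold for the combined comparison and continues: "An equivalent boundary for interim Z-test value is 0.253 (interim P>0.800". It also gives a B-value of 0.179 and a drift estimate of 0.358 as equivalents.

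**The concern.** Conditional power is not a function of the interim data alone. It also needs an assumed drift, the expected value of the final Z statistic. A CP threshold and a Z threshold are the same rule only at one particular drift. The plan names the source of the drift (the design assumption) but gives no number for it. If the CP figure does not match the Z figure at that drift, the external statistician has two stopping rules described as one, and for some interim results they give opposite recommendations. The rule can end the trial, so this should be settled before anyone sees unblinded data.

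**Working it through.** **Inputs.** Two-sided alpha 0.05 and power 85% (Sample Size Calculation). Information fraction t = 0.5, because the look is at 50% of patients. Critical value ZF = 1.947, CP boundary 0.30 and Z boundary 0.253 (Futility Interim Analysis Plan and item 1). The plan does not state the drift. Taking the 85% power at face value, θ = 1.960 + 1.036 = 2.996.

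**Step 1: reproduce the plan's other figures.** With √0.5 = 0.7071:

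- B-value: 0.253 × 0.7071 = 0.179 (stated 0.179).
- Drift estimate: 0.253 / 0.7071 = 0.358 (stated 0.358).
- Null stopping rate: Φ(0.253) = 0.600 (stated 60%).
- Interim Z has mean θ√t = 2.119 under the alternative, so the interim false-negative rate is Φ(0.253 − 2.119) = Φ(−1.866) = 0.031 (stated 3.1%).
- Bivariate normal for interim and final Z, correlation √0.5, cutoff 1.947: continue-and-fail 0.123 (stated 12.3%); power 0.846 (stated 84.6%); upper-tail error under the null, with the stop followed, 0.0250.

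These all agree, so the boundary was evidently built at θ = 2.996 with Z = 0.253.

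**Step 2: CP at that boundary.**

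CP(Z) = 1 − Φ( (ZF − Z√t − θ(1 − t)) / √(1 − t) )

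At Z = 0.253: (1.947 − 0.179 − 1.498) / 0.7071 = 0.270 / 0.7071 = 0.382, and 1 − Φ(0.382) = **0.351**. The plan says 0.30. With 1.960 in place of 1.947 the result is 0.345.

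**Step 3: the Z that gives CP = 0.30.** The argument must be 0.524, so Z√t = 1.947 − 1.498 − 0.524 × 0.7071 = 0.078 and Z = 0.078 / 0.7071 = **0.110**. There the null stopping rate is Φ(0.110) = 54.4% and the interim false-negative rate is Φ(0.110 − 2.119) = 2.2%. Overall power is 84.9%.

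**Step 4: how often the two rules disagree** (0.110 < Z ≤ 0.253; Z stops, CP continues).

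- Under the null: 60.0% − 54.4% = 5.6%.
- Under the design alternative: 3.1% − 2.2% = 0.9%.

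**Step 5: could another drift rescue 0.30?** CP = 0.30 at Z = 0.253 needs θ = 2.795, which is 79.8% fixed-sample power. At that drift the interim false-negative rate is 4.2% and overall power is 79.4%, which contradicts the stated 3.1% and 84.6%.

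**Step 6: the listed sample-size inputs taken literally.** The mean of six AR(1) measurements with correlation 0.5 has variance 14.0625 / 36 = 0.3906 in SD² units. The standard error of the group difference is √(0.3906 × (1/24 + 1/48)) = 0.15625, so θ = 0.3 / 0.15625 = 1.92 and fixed-sample power is about 48%, not 85%. CP at Z = 0.253 is then 0.127. With 80 patients at 2:1, θ = 2.024 and CP is 0.142. This is a separate sample-size problem. It matters here because the plan sends the reader to that paragraph for the drift.

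**Step 7: the P-value gloss.** Z = 0.253 has two-sided P = 0.800 and one-sided P = 0.40. A two-sided P above 0.800 holds only for Z between −0.253 and 0.253. An adverse interim Z of −1.5, for example, has two-sided P = 0.134 and would not meet it, although it clearly meets the signed bound.

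**The case against.** The strongest reply is that the Z, B-value and drift-estimate bounds are numeric, mutually consistent and need no assumed drift. A statistician can simply use them, and Section 9 does offer the B-value bound as an alternative form. That stands, and it is why the Z bound should be kept and the CP figure corrected. It does not remove the conflict, because CP is the criterion stated first, both in the description of the boundary and in item 1.

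It may also be said that 0.3 is a rounded figure. At the plan's own critical value CP is 0.351, which does not round to 0.3, and item 1 writes the threshold as 30%. Only with 1.960 substituted does 0.345 round to it.

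Item 1a mentions an adjusted power of 80%, and an 80%-power drift does give CP close to 0.30. But item 1a concerns the per-dose check, and that drift does not fit the combined-group error figures (Step 5). The CP point is therefore not raised against item 1a.

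Finally, the consequence is small in what is described as a pilot. At the boundary's own drift that is correct.

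**Conclusion.** The stated equivalence is wrong. Under the drift that reproduces every other boundary figure, Z = 0.253 corresponds to CP of about 0.35, and CP = 0.30 corresponds to Z = 0.110. The size is modest: opposite recommendations in 5.6% of null trials and 0.9% under the design alternative, with power 84.6% or 84.9%. It merits correction because a stopping threshold is wrong as written and the repair is cheap. The result assumes t = 0.5, ZF = 1.947 and a drift of 2.996 back-solved from the stated 85% power.

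Two stronger readings are tempting, and the documents do not support them.

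- A reader might infer from CP = 0.127 that the boundary is grossly miscalibrated. That figure reflects the sample-size inputs failing to give 85% power, which is a different defect. The agreement in Step 1 shows that the boundary was not built on those inputs.
- A reader might infer that the mismatch endangers the 5% error rate. With the stop followed at 1.947, upper-tail error is 0.0250 under the Z rule and 0.0253 under the CP rule, and the two-sided total is well under 5%. Nothing here requires a different final critical value.

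**What to change.** 1. For the combined comparison, make the signed bound Z ≤ 0.253 (B ≤ 0.179) the operative futility rule.
2. Restate the matching CP as about 0.35, and write the drift used to compute it (2.996) into the plan as a number before unblinding.
3. Replace the two-sided P > 0.800 beside that bound with one-sided P > 0.40, or delete it.
4. Before settling item 2, reconcile the inputs under Sample Size Calculation with the 85% power claimed from them. If the listed inputs stand, the drift is not 2.996: CP at Z = 0.253 becomes 0.127 (72 patients) or 0.142 (80 patients), and the 3.1%, 12.3% and 84.6% must be recalculated.

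Items 1 to 3 are wording changes that leave the Z boundary, the 1.947 critical value and the stated 84.6% power as they are. Item 4 needs one sample-size recalculation, which the separate power problem requires in any case.

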Specific Aim #3:Establish the time needed to reach peak efficacy. Duration of treatment in the original study was three weeks, and significant therapeutic benefit was observed only at the three-week endpoint but not earlier. In the proposed study, subjects will receive study drug for 6 weeks and we expect that the size of the therapeutic benefit of oxytocin will increase from 3 to 6 weeks.

Specific Aim # 4: Investigate the possible cognitive effects of intranasal oxytocin. In the pilot study, oxytocin significantly improved short term recall performance in the California Verbal Learning Test. This raises the possibility that chronic oxytocin will improve cognitive deficits associated with schizophrenia. This study will test this hypothesis using the Computerized Multiphasic Interactive Neurocognitive DualDisplay™ System (CMINDS®) and Mayer-Salovey-Caruso Emotional Intelligence Test: Managing Emotions (MSCEIT™ ME).

Specific Aim #5: To determine if daily intranasal oxytocin is sufficiently safe, feasible and acceptable to patients to warrant further clinical development. Information derived from this study will inform development of oxytocin not only for schizophrenia but other potential neuropsychiatric disorders.

Specific Aim #6: The objective of the study is to compare the efficacy of intranasal oxytocin versus intranasal placebo to improve symptoms in schizophrenia patients who have residual symptoms despite being on adequate treatment with antipsychotic medication. Improvement will be measured by total score in the Positive and Negative Syndrome Scale (PANSS).

Specific Aim #7: To determine if oxytocin-induced enhancement of mu-rhythm suppression of 'mirror' neurons in schizophrenia patients can serve as a predictive biomarker of individual clinical response to this neurohormone.

Secondary objectives include:

 To evaluate the efficacy of intranasal Oxytocin as measured by change in the total CGI-Severity and Improvement scores

- To evaluate the efficacy of intranasal Oxytocin as measured by change in the total GAF score
- To evaluate the efficacy of intranasal Oxytocin as measured by change in the total scores of HAM-A.
- To evaluate the efficacy of intranasal Oxytocin on self-rated social anxiety as measured by change in the total Social Phobia Inventory (SPIN).
- To evaluate the efficacy of intranasal Oxytocin as measured by change in the total Calgary Depression Scale for Schizophrenia (CDSS) scores.

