- 2. Subjects will be given a diary card by the study staff to mark each use of the study drug in between site visits to the study site. This is to help subjects track study drug use. Subjects will be instructed to return study drug nasal spray bottles, used or unused, to the site at each visit along with the diary card.
- 3. Each bottle will re-weighed after return to estimate the amount of fluid remaining

STUDY DRUG:

Intranasal oxytocin is FDA approved as a lactation aid and was commercially marketed (Syntocinon®, Novartis) in the US up to the 1990's. It continues to be marketed commercially by Novartis in Europe and elsewhere. Oxytocin powder (Pictocin, Novartis) is readily available in the US and is used for intravenous

administration as a paruition stimulant in pregnant women. Both intravenous and intranasal oxytocin are well tolerated and safe (Hoover RT 1971) (see risk section of this Research Plan).

This study will use oxytocin powder supplied by Spectrum Laboratories and UCSD Investigational Drug Service (IDS) will make formulate both the Oxytocin and Placebo.

-Chlorbutanolhemihydrat 2.5mg -Methyl-4-hydroxybenzoat 0.4mg -Propyl-4-hydroxybenzoat 0.2mg -Dinatriumphosphatanhydricum 1.9mg -Acidumcitricumanhydricum 2.56mg 5.0mg -Na-Sorbit -Sorbitol 70% 25.0 mg -Glycerin 85% 25.0mg -Aqua pur. q.s.

Comment: 1 IU is 1.7 micrograms oxytocin and 1 puff is 12 IU (=20.4 micrograms oxytocin)

STATISTICAL CONSIDERATION

Our primary analysis will be the comparison of subjects on oxytocin with subjects on placebo using a mixed model repeated measures analysis (MMRM). If this comparison is statistically significant then we use a linear contrast to investigate the dose-response between 84 IU (42 IU bid) and 168 IU (84 IU bid). We also have introduced an adaptive design that is consistent with FDA guidance for phase 2 studies when dosing groups are unclear (2010).

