Analysis Methods: The primary population for efficacy analyses includes all randomized subjects based on the intention-to-treat principle. The population for safety analyses will include all subjects who receive at least one dose of study medication. In the primary analysis, we test the hypothesis of difference in PANSS total change score (Week 6) between the combined oxytocin and placebo groups with adjustment for baseline score using a likelihood-based mixed-effects model for longitudinal data analysis (MMRM LDA) (Fitzmaurice and Ware, 2004). The MMRM LDA model can accommodate incomplete data under the assumption of ignorable attrition (see below under Missing Data). The same MMRM LDA model will be applied to evaluate the dose-response relationship using a linear contrast for the placebo and oxytocin dose groups, comparisons of treatment groups over time using treatment-by-visit (categorical visit variable) interaction term, and the trajectories of treatment responses over time based on time slope computed for each subject (continuous time variable).

Secondary efficacy measures will be the PANSS positive symptom and negative symptom subscales, PANSS general psychopathology subscale, CGI-S, CGI-I HAM-A, CCDS, GAF, cognitive scales as with the primary endpoint using the same MMRM LDA analyses. No multiplicity adjustment will be made in the secondary analyses. Appropriate descriptive statistics with 95% confidence intervals will be provided within and across treatment groups. Normal assumption will be checked and nonparametric alternatives will be considered if the assumption is seriously violated.

Mediators and baseline moderators of treatment effects on efficacy outcome measures will also be explored (Kraemer et al., 2006). The significance of moderator effects due to baseline characteristics (age, gender, initial

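### The primary test is the Week-6 difference, but the stated power, the conditional-power assumption and the interim error rates are built on a time-averaged effect

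*Combined protocol and SAP*

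**What the plan says.** All statements are in section 9 of the combined protocol and SAP unless noted.

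- **Analysis Methods.** In the primary analysis "we test the hypothesis of difference in PANSS total change score (Week 6) between the combined oxytocin and placebo groups", adjusted for baseline, from a likelihood-based mixed model. The dose-response contrast, treatment-by-visit comparison and time slopes are listed as further uses of the same model. No time-averaged test is listed.
- **Sample Size Calculation.** "The primary efficacy measure will be change in PANSS total score from baseline to each visit". The sample of 24 placebo and 48 oxytocin subjects is said "to achieve 85% power to detect an effect size of 0.3 for time-averaged main treatment effect", "using 6 repeated measurements having a AR(1) (first order autoregressive) covariance structures and assuming the correlation between observations on the same subject is 0.5", at two-sided alpha 0.05.
- **Futility Interim Analysis Plan.** Stop if conditional power falls below 0.30 under the original design assumption, with a pointer back to the Sample Size Calculation. The equivalent interim Z is given as 0.253 and the final critical value as 1.947. Overall power is 84.6%, with false-negative rates of 3.1% at the interim and 12.3% at the end. The contrast that supplies the interim Z is not named.
- **Section 6, Specific Aim #3.** The earlier study saw benefit only at its three-week endpoint, and here "we expect that the size of the therapeutic benefit of oxytocin will increase from 3 to 6 weeks".
- **Missing Data.** Further model details are deferred to a Statistical Analysis Plan. Nothing in the text supplied reconciles the two contrasts.

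**The concern.** A "time-averaged main treatment effect" and a Week-6 difference are two contrasts from the same model. Averaging six correlated visits shrinks the standard error, and a single-visit contrast gets no such gain. The effects also differ if benefit builds over time, which Aim #3 expects. Power worked out for one contrast says nothing direct about the other.

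Two things are at stake. The first is whether the trial has the power that readers are told it has for its declared primary test. The second is the futility rule: its 3.1% risk of stopping wrongly depends on the drift of the statistic used. If the interim Z is a Week-6 statistic with a smaller drift, a trial of an effective treatment would be stopped more often than stated.

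**Working it through.** **Inputs from the plan.** 24 placebo and 48 oxytocin; d = 0.3 as a time average; 6 visits; AR(1) with correlation 0.5; two-sided alpha 0.05; interim at 50% of patients; interim Z boundary 0.253; final critical value 1.947. **Assumptions of this check.** Normal approximation, no dropout, information fraction 0.5. The baseline correlation r and the shape of the time course are also assumed, because the plan gives neither.

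**1. The plan's interim figures.** 85% power at two-sided 0.05 implies a drift of 1.960 + 1.036 = 2.996. At information 0.5 the interim Z has mean 2.996 × √0.5 = 2.119.
- P(Z < 0.253) = Φ(0.253 − 2.119) = 3.1%.
- P(Z < 0.253) under the null = Φ(0.253) = 60%.
- With final critical value 1.947, the bivariate normal gives 84.6% power and 12.3% final false negatives.

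These reproduce the stated figures, but only if the interim and final Z are the same contrast and its true drift is 2.996.

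**2. The two contrasts.** SE for one visit, in SD units, is √(1/24 + 1/48) = 0.25.
- Variance of the six-visit mean: [6 + 2(5×0.5 + 4×0.25 + 3×0.125 + 2×0.0625 + 0.03125)]/36 = 14.0625/36 = 0.3906, so SD 0.625.
- SE of the time-averaged contrast: 0.25 × 0.625 = 0.156, against 0.25 at Week 6.
- Correlation of the two statistics: [(1 + 0.5 + 0.25 + 0.125 + 0.0625 + 0.03125)/6]/0.625 = 0.328/0.625 = 0.525.

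**3. Week-6 power.** Drift = d/(0.25√(1 − r²)).

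| Time course (assumed) | Week-6 d | r = 0 | r = 0.5 | r = 0.7 |
|---|---|---|---|---|
| Constant at 0.3 | 0.30 | drift 1.20, 22% | 28% | 39% |
| None before Week 3, then constant, average 0.3 | 0.3 × 6/4 = 0.45 | drift 1.80, 44% | 55% | 71% |
| Linear rise, average 0.3 | 0.3 × 6/3.5 = 0.51 | drift 2.06, 54% | 66% | 82% |

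The r = 0 column matches the sizing assumption, which mentions no baseline adjustment. If AR(1) at 0.5 also ran back to baseline, the baseline to Week-6 correlation would be 0.5⁶ = 0.016 and adjustment would gain nothing.

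**4. The opposite direction.** If 0.3 is the Week-6 effect and the rise is linear, the time average is 0.3 × 3.5/6 = 0.175. Time-averaged power is then 20% (0.175/0.156 = 1.12).

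**5. Interim behaviour for a Week-6 Z, r = 0.**
- Drift 1.20: interim mean 0.849, P(Z < 0.253) = Φ(−0.596) = 28%. Overall power is 22% and final false negatives 50%.
- Drift 2.06: interim mean 1.455, P(Z < 0.253) = Φ(−1.202) = 11%. Overall power is 54% and final false negatives 35%.

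The plan states 3.1%, 84.6% and 12.3%.

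**The case against.** The strongest reply is that the deciding test is already named. Analysis Methods specifies Week 6, and no section makes a time-averaged test primary; that effect appears only as a sizing assumption. This stands. A reader might infer that the plan holds three rival primary effects, so that two analysts could follow it to opposite conclusions. The documents do not support that. Change to each visit describes the repeated outcome and fits either contrast, and the opening statement of the primary analysis is silent on the time point rather than contradictory. Following Analysis Methods gives one test, so the mismatch does not by itself inflate Type I error.

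A reader might also infer that the interim uses a different contrast from the final test. The plan defines conditional power as the chance that the final results are significant, and times the look on completed six-week follow-up. Both fit a Week-6 contrast. The interim Z is unspecified, not defined differently. Its design assumption is still borrowed from the time-averaged calculation.

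Third, 22% is a scenario and not a consequence of the plan. Under the growth that Aim #3 expects, an average of 0.3 means a larger Week-6 effect, and with a favourable baseline correlation of 0.7 the linear case reaches 82%. That is fair, but the plan states neither assumption.

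Finally, the plan gives a single-measurement figure (d = 0.5, 80 patients at 2:1, same alpha and beta), which could be read as covering Week 6. It does not rescue the claim: 0.5/√(1/26.67 + 1/53.33) = 2.11, or 56% power.

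**Conclusion.** The point holds in this form: the primary test is at Week 6, while the 85% and 84.6% power, the conditional-power design assumption and the 3.1% and 12.3% error rates rest on a time-averaged d = 0.3. They do not describe the declared test.

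Unadjusted Week-6 power is about 22% at d = 0.3 and about 54% under an assumed linear rise to 0.51. The chance of a futility stop under those effects is about 28% and 11%. The baseline-adjusted figures depend on an r that the documents do not give, and should not be set beside an unadjusted time-averaged figure. Pilot status does not remove the issue, because the trial has a formal alpha, an adjusted critical value and a stopping rule.

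That the 85% does not reproduce even for the time-averaged effect (0.3/0.156 = 1.92, or 48%) is a separate finding and carries no weight here.

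**What to change.** 1. Keep the pooled oxytocin minus placebo difference at Week 6, from the baseline-adjusted mixed model, as the single primary test. Say so in the opening statistical statement and in the Sample Size Calculation as well.
2. State that the interim Z, B-value, drift estimate and conditional power use that same contrast.
3. State a Week-6 effect size, with the time course and baseline correlation it assumes. Restate power, design drift, the futility boundary and the interim and final error rates for it.
4. List the time-averaged effect as secondary.

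This should be settled before the unblinded interim, so that the contrast is not chosen with data in hand. It changes protocol and SAP wording only. The downside is a less favourable stated power, which may prompt questions about sample size.
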